Social-demographic data (age, gender, marital status, exercise habits, living conditions, and level of education) will be collected. The participants' health-related information will also be collected, including their morbidities, cognitive status, fall history, and medications taken in the past 12 months.

The feasibility assessment includes the ease of recruitment, the acceptance rate, the dropout rate, the engagement of PWD when attending the Tai-chi training sessions, the adherence to practising Tai-chi at home and at training sessions, the occurrence of adverse events, and feedback from the participants (caregivers) as well as the Tai-chi instructor.

- **Ease of recruitment** – if any difficulties encounter during the recruitment phase will be recorded to consider for improvements in the future main study.
- **Acceptance rate** refers to the proportion of subjects who provide proxy consent to join the study over the eligible participants will be calculated for the acceptance rate.

- Dropout rate – percentage of participants withdrawing from the study will be recorded and the reasons for withdrawal will be asked
- Engagement of participants when attending the Tai-chi training sessions will be assessed by the Non-pharmacological Therapy- Experience Scale (NPT-ES). This scale was developed by Muñiz et al in 2011 with an aim to measure the immediate emotional and social effects of any kind of non-pharmacological interventions delivered to PWD³³. It is a 5-item scale which includes participation, pleasure, relationship with others, displeasure and rejection (the last two are reverse items). Each item is rated on a 4-point scale from 0 =Never to 3= Always. By summing up all five item scores to get the total score ranged from zero to fifteen, higher scores indicating more positive experience. All Tai-chi training sessions will be video-taped. The well-trained research assistant (RA) will assess the engagement of each participant during each training session based on both real time and the video observations. The Tai-chi instructor will also be required to comment on the engagement of each participant in terms of whether or not a particular participant can follow each Tai-chi step appropriately based on her observations during the training sessions.

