- Exercise adherence will be assessed weekly based on the caregiver report in an exercise diary on the days and duration that the participant practises Tai-chi. This diary will be collected every week during the 16-week training period. Weekly phone calls will be made by an RA to remind the participants to return the diary as well as to verify the records. Attendance in the Tai-chi training sessions will also be recorded as evidence of adherence to the training programme.
- The occurrence of adverse events will be recorded which include the date, the time, the unanticipated bodily response and symptoms (e.g. fall, fatigue, dizziness), and the immediate treatment provided.
- Collection of feedback from all stakeholders – Feedback from participants and their caregivers will be collected by focus group within two weeks after completing the entire Tai-chi programme. An individual interview will be conducted to collect opinions from the Tai-chi master. The interview guides for different stakeholders will be set up. A panel of experts will be invited to review the interview guide to evaluate the appropriate of the questions. The interview will be audiotape recorded and transcribed verbatim.

Preliminary outcomes assessment: motor performance

- Mobility will be assessed by the Timed-up-and-Go (TUG) test^{34,35}. The time taken by participants to execute the tasks – stand up from a standard chair, walk three meters, turn around, walk back to the chair and sit down will be recorded in seconds.
- Functional limb muscle strength will be assessed the Timed-Chair-Stand (TCS) test³⁶. Each participant will be asked to sit at the front edge of a standard chair with their arms crossed, and instructed to stand up fully and sit down five times as quickly as possible. Time to complete this task will be recorded.
- Dynamic bilateral stance balance will be assessed by the Functional Reach (RF) test³⁷. Participants will stand beside a wall with their feet apart for about 10 cm and raise their dominant arm to 90 degrees. They will then be instructed to lean forward as far as possible with the hand remaining at shoulder level. The FR score will be the additional reach of the raised hand from the starting position in cm.

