- Dynamic single leg standing balance will be assessed by the Step Test (ST) test³⁸. Participants will stand with their feet parallel and apart for about 10 cm. A block / step with 7.5 cm height will be placed 5 cm in front of the participants. They will be instructed to place the whole foot onto the block, then return it fully back down to the floor repeatedly as fast as possible for 15 seconds. Each leg will be tested separately, and performance on the left or right side with the least number of steps will be the result.

The number of falls will be also recorded by the caregivers and the participants in a monthly falls calendar, in which they will note down any fall accidents that have happened to the participant during the 16-week study period. Monthly phone calls will be made by an RA-observer to remind the participants to return the calendar as well as to verify the records. A fall will be defined as “an unexpected event in which participants come to rest on the floor or lower level⁴¹.” This will be used to guide the participants (caregivers) in recording their fall accidents. The severity of the injuries will also be recorded.

Procedures (randomization, allocation concealment, blinding)

After ethical approval has been obtained, all potential participants will be screened for their eligibility to participate in the study. The participants and their caregivers will then be interviewed to obtain their proxy informed consent, socio-demographic data, and baseline assessment. After that, the four community centres will be randomized to the control or the experimental groups. The participants from each centre will be placed into their centre’s corresponding group to avoid ‘contaminating’ other participants. The changes in the above mentioned preliminary outcome scores from the baseline to interim assessment at Week 8 (T1:Mid-term of intervention) and intervention effects at immediate (T2) after completion of the 16-week interventions will be compared between the groups by the RA-observer.

Twenty participants from the Tai-chi group will be randomly selected to join the focus groups within two weeks after completing the entire programme. Each focus group will contain between 5 and 10 people. The Tai-chi instructor will also be interviewed individually. All interviews will be conducted by the PI in the community health centres to collect the opinions on the design of the intervention. (Appendix II: Timeline of the study)

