Official Title: The Effects of Simplified 10-step Tai-chi Programme
on the Motor Performance and Fall Prevention of Community-
dwelling Older People With Dementia: a Pilot Cluster Randomized
Control Trial

Date of the document: 16 May 2016

**The effects of a simplified 10-step Tai-chi programme on the motor performance and fall prevention of community-dwelling older people with dementia (PWD):
A pilot cluster RCT study**

Statistical Analysis

SPSS will be used for data analysis. Descriptive statistics will be generated for the demographic data. Normality assumptions for the variables will be checked. The paired t-test or Wilcoxon's signed rank test will be used to examine any significant difference in outcome measurements in the experimental group before and after the implementation of the combined intervention. Student's T-test or the Mann-Whitney U test will be used to examine any significant differences between the control and experimental groups in terms of the outcome variables. For categorical and dichotomous outcome variables, a χ^2 test will be used to identify any significant differences between the groups. A p-value < 0.05 will be considered statistically significant. Mixed effect modelling (MEM) will be further used to measure changes in the outcome measures after intervention with respect to its baseline, and to see the effectiveness of the intervention. Multiple imputations will be adopted to manage missing data.

All interviews will be transcribed and analyzed by content analysis so as to understand participants', caregivers' and the Tai-chi instructor's opinions about the intervention. Coding will occur independently by two members of the research team. Differences in coding between the independent coders will be resolved through discussion between the coders

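### The planned between-arm test of falls leaves the collected fall history unused, and the SAP does not exclude falls from its before/after tests

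*SAP*

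**What the plan says.** **Baseline falls information.** The Protocol (Instruments and Measures) collects health-related information, "including their morbidities, cognitive status, fall history, and medications taken in the past 12 months". The 12 months may govern the whole list or only the medications. The Protocol does not say whether fall history is a count or a yes/no item. It describes no run-in or prospective baseline count.

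**Falls during the study.** The same section states: "The number of falls will be also recorded by the caregivers and the participants in a monthly falls calendar". The calendar covers the 16 weeks of the study.

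**Analysis.** The SAP's Statistical Analysis text, which the Protocol shares, does not mention falls. It gives three generic rules for numerical outcomes:
- a paired t or Wilcoxon test, before against after, in the experimental arm;
- between arms, Student's t-test or "the Mann-Whitney U test will be used to examine any significant differences between the control and experimental groups";
- a mixed model: "Mixed effect modelling (MEM) will be further used to measure changes in the outcome measures after intervention with respect to its baseline", and also to judge effectiveness.

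It names no covariate, count distribution or person-time offset. It makes no exception for falls.

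**The concern.** Fall prevention is in the trial's title, so a falls result is likely to be reported and carried into planning the main study that the Protocol mentions. Two gaps affect that result.

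First, people who have fallen before can be expected to fall more. Only four conveniently sampled centres are randomised, so the arms may differ in their share of prior fallers. An unadjusted test passes any such difference straight into the falls comparison, although the variable that would help is already collected.

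Second, an analyst who applies the paired test to every outcome has nothing to pair with the 16-week calendar count except recalled history. The two differ in method and, very probably, in window. The test would then largely measure the difference in windows.

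**Working it through.** **The plan's own figures.** The documents give no fall rate, dispersion, prevalence of prior fallers or power. The 30 per group rests on a pilot-study reference, so there is no falls calculation to reproduce. The 16-week window agrees with the Protocol's 56 practice hours: 16 × (2 × 1 + 3 × 0.5) = 56.

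**1. Window mismatch within one arm.** With a constant fall rate, the apparent change is 1 - 16/(weeks recalled).
- 12 months: 1 - 16/52 = 69.2% apparent drop.
- 6 months: 1 - 16/26 = 38.5% apparent drop.
- 3 months: 1 - 16/13 = -23%, an apparent rise.
- Yes/no history: no change in count can be formed.

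A simulation with no treatment effect took 30 people per arm, Poisson falls with gamma frailty of shape 1, a 12-month history, no clustering and 2,000 runs per setting:

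| Assumed falls per person-year | Paired t, p < 0.05 | Wilcoxon, p < 0.05 | Between-arm t-test on change, p < 0.05 |
|---|---|---|---|
| 0.5 | 58% | 59% | 4.0% |
| 1 | 87% | 88% | 4.4% |
| 2 | 99% | 99% | 4.7% |
| 3 | 99.9% | 99.9% | 4.1% |

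With equal 16-week windows, paired rejection returned to about 4%. The artefact therefore belongs to the within-arm test (or a raw time term), not to the arm contrast.

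**2. When the arms differ in underlying rate.** Take a control rate of 2 per year and no effect. The control change is 2 × (16/52 - 1) = -1.38 falls. If the Tai-chi arm's rate is 0.7 or 1.5 times that, its change is -0.97 or -2.08. The difference in change is then about +0.41 or -0.70, and the simulation rejected in 12% and 17% of runs. The unadjusted comparison of 16-week counts rejected in 11% and 15%.

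**3. Imbalance in prior fallers.** Suppose prior fallers fall *h* times as often, and make up 40% of the Tai-chi arm and 60% of the control arm. With no effect, the rate ratio is (0.4*h* + 0.6)/(0.6*h* + 0.4):
- *h* = 2: 1.4/1.6 = 0.875
- *h* = 3: 1.8/2.2 = 0.82
- *h* = 4: 2.2/2.8 = 0.79

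With 30 independent people per arm and 50% prevalence, a gap of at least 6 of 30 (20 points) in either direction has probability 0.155. Variation between centres would raise it.

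**4. Gain from adjusting for prior faller, yes/no.** Negative-binomial simulations used assumed values of *h*, fall rate and centre SD in prevalence (0 to 1 on the logit scale). They compared the root-mean-square error (RMSE) of the log rate ratio with and without the covariate.
- Perfectly measured history: about 0 to 20% smaller, and about 1 to 8% with no centre variation.
- Most favourable corner (4 falls per year, *h* = 4, centre SD 1): one set of runs went from 0.464 to 0.344, which is 26%.
- 15% of people misclassified: between 2% worse and 9% better.
- 25% misclassified: between 2% worse and 4% better.

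**5. Amount of data.** At 1 to 4 falls per person-year, expected falls per arm are 30 × 16/52 × rate = 9 to 37. Any rate ratio will be imprecise.

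**The case against.** A reader might infer that the SAP's change-from-baseline analyses will report a 69% fall reduction whatever Tai-chi does. The documents do not support that.
- No sentence applies those analyses to falls. The Protocol's Procedures section ties change from baseline to the preliminary outcome scores, and the matching heading is "Preliminary outcomes assessment: motor performance". Falls are described after the four motor tests and have no Week 8 or end-of-programme score.
- The 12-month recall is one reading of an ambiguous list.
- The mixed-model sentence also serves to judge effectiveness. In an arm contrast the window mismatch cancels when underlying rates are similar. The paired-test rule is where the risk lies.

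These points stand, and they confine the artefact to a conditional risk. They do not remove it, because nothing excludes falls from the paired test.

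A second objection is that comparing randomised arms without covariates is not an error, that the mixed model's covariates are simply unspecified, and that the gain rests on assumed inputs. This also stands. People with dementia and their caregivers may recall falls poorly, and the gain then almost vanishes. So adjustment is an improvement, not the repair of a fault.

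Finally, this is a feasibility pilot whose stated aim names motor performance, not falls, and four centres cannot support a confirmatory falls result. That limits how much weight the point deserves.

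**Conclusion.** The concern holds in a limited form, as a free improvement. The SAP's stated between-arm test makes no use of fall history for the falls count, and its generic paired test leaves falls in.

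- **Firm:** no baseline falls measure other than history is described, and the named between-arm tests are unadjusted.
- **Conditional:** the 69% needs a constant rate, a 12-month count and a within-arm comparison of raw counts. It is not a planned result and not a bias in the treatment contrast when the arms have similar underlying rates.
- **Assumed:** the rate ratios of 0.875 to 0.79 need a 40% v 60% split and *h* of 2 to 4. The RMSE gain of about 0 to 20% needs well-measured history and assumed fall rates, with larger gains only in the most favourable corner. It is near zero with poor recall.

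**What to change.** Add to the SAP, and match it in the Protocol's Statistical Analysis section:

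> Falls are not tested before against after, nor analysed as change from baseline. Calendar falls over the 16 weeks are compared between arms by a rate ratio with 95% CI from a count model with log person-time as offset, baseline fall history (faller yes/no, over a stated recall period) as a covariate, and allowance for the four randomised centres. The result is descriptive.

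State the recall period and the yes/no definition in Instruments and Measures, so that the reference to 12 months is no longer ambiguous. Name the method used for the centres. With four centres in two arms, a centre-level comparison has only 4 - 2 = 2 degrees of freedom, so an interval that treats the 60 people as independent would be too narrow if fall rates vary between centres. Falls and person-time should also be listed by centre.

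The cost is a short SAP paragraph and one clarifying line in the Protocol. It needs no new data. The covariate is one extra model term, and the simulated loss when history is poorly recalled is about 2% at worst.
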